4 STUDY ENROLLMENT AND WITHDRAWAL

Study population will predominantly be from outpatient clinics. Those identified as CRAG+ by lab test will typically be HIV-infected outpatients presenting for routine care. However, there will be some who present with complaints of feeling unwell.

4.1 Subject Inclusion Criteria

• Blood CRAG test positive

4.2 Subject Exclusion Criteria

• Age <18 years

Rationale for Criteria:

This project will generate an epidemiological dataset and will then explore the primary endpoint for pre-specified subgroups, along with operational challenges amongst specific subgroups.

STUDY EVALUATIONS 5

We will collect 3 types of data: patient-level, clinic-level, and laboratory-level.

Patient-level data

Chart review will occur approximately 3 times over a 6 month period, with the goal of capturing the patient-level information on CRAG+ persons. Timing of these chart reviews will be variable.

The chart abstractor will ensure that the subject has a positive CRAG result. If so, additional clinical information will be extracted from the chart (see below).

Informed consent will not be obtained for this study, as we are retrospectively collecting demographics and outcomes for CRAG+ and CRAG- patients in routine care. Please see Informed Consent section below.

Baseline demographic information will be obtained, including age, sex, date of birth, location, distance from clinic. Thereafter information about CRAG screening will be obtained. Namely, whether CRAG results were returned to the medical chart and how the healthcare provider acted on these results. If symptomatic, were they offered an LP? If asymptomatic were they prescribed fluconazole? What were the doses and dates of fluconazole therapy, and were there any side effects. Timing of initiation of ART and active treatment for TB will be obtained from the chart. Survival status, along with the date that the patient was last known to be alive will also be collected.

	ecieu
Evaluations	Monitoring Visit
CRAG+, titre	х
CD4 count	Х
Baseline demographic data	Х
If symptomatic, receipt of LP	х
If asymptomatic, receipt of fluconazole	х

Patient-level	data	to be	collected

Evaluations	Monitoring Visit
Completion of fluconazole	Х
Initiation of ART (timing)	Х
Concurrently on TB treatment	Х
Incidence of cryptococcal Meningitis	Х
6-month retention in care	х
6-month vital status	Х

5.1 Clinic Evaluations

Clinic-level factors will be collected to further understand challenges to CRAG screening. This information will be extracted from existing data systems, and from primary data collection. For example, we will collect

- Distance from clinic to nearest NHLS CD4 lab already mapped out by NHLS
- Number eligible for CRAG screening at clinic site
- Number CRAG screened, by clinic site
- Number who received TB screening
- Timing from CD4 testing to receipt of CRAG result
- Proportion who required LP, and had LP performed
- Acceptability of LP by patients
- Resources for LP performance
- Healthcare worker training (nurses, doctors, counselors, pharmacists) by clinic site

- Clinic standard of care for initiation of ART (test and treat vs. wait for CD4 results)
- Frequency of fluconazole stock outs

5.2 Laboratory Evaluations

Information from each NHLS CD4 laboratory will be obtained to further understand barriers to reflex CRAG screening. Such information may include:

- Number of CD4<100 cells/uL per week/month
- How CRAG screening performed (batched, performed daily)
- Ease of performing CRAG titres in real-time (prospectively)
- Procedures after CRAG+ result identified

6 ASSESSMENT OF SAFETY

As we are retrospectively monitoring outcomes in routine care, there will be no assessment of safety. CRAG screening and preemptive treatment have previously been studied to be safe and efficacious. This is now standard of care in South Africa; no additional safety monitoring will be pursued.

7 CLINICAL MONITORING

N/A

7.1 Site Monitoring Plan

N/A

8 STATISTICAL CONSIDERATIONS

Primary Endpoint

- 1) 6-month cryptococcal meningitis free survival
 - Those who die of any cause are failures
 - Those developing symptomatic meningitis are failures

8.1 Statistical Analysis Plan

The rate (with 95% confidence interval) for the primary and secondary events will be estimated overall and for pre-specified subgroups during the first 2 years of the study. Those rates will subsequently be compared with the rates after programmatic changes have been made (during years 2-5) to increase the effectiveness of the national screening program.

For the subgroups we will also use time-to-event methods to compare the primary and selected secondary endpoints. The table below reports detectable hazard ratios for the primary event with 80% and 90% power, assuming a two-sided alpha=0.05, 70% CM-free survival in the control group, and the stated number of subgroup participants. For example, if CSF CRAG titre data are available for 1200 participants (with 300 having a titre \geq 160), then we can detect a hazard ratio as small as 1.37, for an almost 10% difference in event-free survival.

Detectable Hazard Ratios for Subgroups					
(Assuming two-sided α =0.05 and 70% event-free survival in the control group)					
		80% Power		90% Power	
	N per		Proportion		Proportion
Subgroup	group	HR	Surviving	HR	Surviving
High CSF CRAG titre	300	1.37	0.61	1.44	0.60
(≥1:160)					
Control	900				
(CSF CRAG titre < 1:160)					

The a priori subgroups of interest are:

- High CRAG titres (\geq 1:160) vs. low titres (<1:160)
- Male vs. Female
- Pregnant vs. Non-pregnant
- Liver Disease (ALT>3x Upper Limit of Normal) vs. No liver disease

- Geographic Location (urban vs. rural)
- Timing of ART Initiation
 - On pre-existing ART
 - Initiated on ART before CD4/ CRAG results are known (same-day ART initiation in the context of universal HIV test-and-treat)
 - ART initiated at 2 weeks
 - ART initiated at >=4 weeks
- Clinic-level outcomes (i.e. cluster) based on proportion of CRAG+ persons receiving Lumbar Punctures.
- Duration of fluconazole use
- Fluconazole secondary prophylaxis vs. none

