 - o Subset of those with cryptococcal meningitis

Primary objective (Years 2-5): To implement and test programmatic interventions to improve 6-month cryptococcal-free survival.

Starting in Year 2, we will use the data generated from the preceding years regarding the barriers in the cascade-of-care to identify areas which may require programmatic interventions to improve 6-month CRAG+ outcomes. Such interventions will be implemented at selected enhanced surveillance facilities to determine their effectiveness (pre/post intervention) as well as compared with facilities without the intervention. The exact intervention(s) to be implemented will be dependent on the challenges observed during the initial surveillance. Examples may include:

Intervention 1: Stratification by CRAG titre

For a subset of CRAG+ persons in the enhanced surveillance cohort, we will perform CRAG titres. We anticipate performing these retrospectively (batched) initially, and then for a short time prospectively to evaluate whether this is feasible in the lab. CRAG titres will not be reported to treating clinicians initially. Once data have been collected in years 1 and 2 regarding outcomes of those with high CRAG titres vs. low CRAG titres, we may then routinely report CRAG titre results with CD4 results. An information sheet may be attached to the lab results educating healthcare workers of the CRAG+ result and suggestions for management. Alternatively, this

information will be included in routine healthcare worker training materials. We may recommend that those with a CRAG titre \geq 160 have a LP performed to evaluate for meningitis, given that these persons are at high risk for meningitis and death. The outcome will be 6-month survival.

We hypothesize those with CRAG titres \geq 160 will benefit from recommended lumbar punctures to detect occult meningitis (defined as CSF CRAG+ and/or culture-positive) in comparison with those who decline LPs. Conversely, we hypothesize those with low CRAG titres <160, do not have a survival benefit when receiving LPs (i.e. due to low prevalence of asymptomatic occult meningitis).

Intervention 2: Healthcare provider training

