- We will create online/digital training programs for laboratory workers, health care providers, and clinic staff regarding CRAG screening and pre-emptive treatment. Alternatively, we will partner with existing initiatives such as Project ECHO (continuing professional education and clinical mentoring via zoom video conferencing). These educational programs will be implemented at clinics to evaluate whether gaps in the cascade of care can be minimized.
- We will create refresher training for lab workers, health care providers, and clinic staff regarding CRAG screening and pre-emptive treatment, and measure if more frequent training sessions improve adherence to national protocols and patient outcome.
- Finally we will create patient education materials in the form of posters that can be hung in clinic waiting rooms, short presentations that can be performed by community healthcare workers in clinic waiting rooms/ as part of focus groups, and digital training programs for patients. We will measure overall clinic adherence to national protocols and patient outcomes. Sample educational materials below.

Intervention 3: Determine benefit of enhanced methods to deliver CD4 and CRAG results

- a) SMS may be used for clinic appointment reminders, medication adherence reminders, and general information, as a potential method to enhance retention in care of CRAG+ persons. SMS may be used by clinics to enhance the cascade of care, for example, to report anticipated fluconazole stockouts, or to remind providers to perform TB screening for those with advanced HIV disease.
- b) Reports for each district and facility managers with line list of CRAG+ patients, and those with a CD4<100 without CRAG testing (compare outcomes in districts/ facilities with Result for Action reports vs. no Result for Action reports)
- Intervention 4: Enhanced antifungal therapy based on CRAG titre. After years 1 and 2, outcomes of those with high/low CRAG titres will have been summarized. We hypothesise that those with high CRAG titres would have higher mortality and would be at higher risk for breakthrough meningitis, as seen in multiple other studies.

If this is the case, we may then select a small number of high volume sites to perform CRAG titres in real time, and recommend enhanced antifungal therapy for those with high CRAG titres. Please note: This will be a separate ethics committee submission and will include informed consent from participants.

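### Section 8.1 names no cluster unit for comparisons of exposures set at facility or district level, so unadjusted error bars would be wrong: modestly at about 3 patients per clinic, seriously between districts

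*Protocol*

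**What the plan says.** **Where the interventions act.** Protocol section 3 (Primary objective, Years 2-5) states: "Such interventions will be implemented at selected enhanced surveillance facilities to determine their effectiveness (pre/post intervention"). The same sentence adds a comparison with facilities that do not have the intervention. Training and patient education are placed in clinics. For Intervention 3(b) the plan is to "compare outcomes in districts/ facilities with Result for Action reports vs. no Result for Action reports".

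**What is measured.** The endpoint in section 8 is 6-month cryptococcal meningitis-free survival of the individual CRAG+ patient.

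**How it is analysed.** Section 8.1 estimates rates with 95% confidence intervals in the first two years and continues: "Those rates will subsequently be compared with the rates after programmatic changes have been made". That is its whole statement on the Years 2-5 objective. The concurrent comparison with facilities lacking the intervention does not appear there. Time-to-event methods are added for subgroups only.

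**Detectable effects.** One table gives "detectable hazard ratios for the primary event with 80% and 90% power", "assuming a two-sided alpha=0.05, 70% CM-free survival in the control group". Its only contrast is titre, 300 against 900 patients.

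**Clustering.** The one mention in section 8.1 is a subgroup entry: "Clinic-level outcomes (i.e. cluster) based on proportion of CRAG+ persons receiving Lumbar Punctures". Urban versus rural is in the same list without that label.

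**The concern.** When an exposure is the same for every patient in a clinic or district, the information about its effect comes mainly from the number of clinics or districts and from how alike outcomes are within them. A comparison of pooled patient rates counts every patient as a separate piece of evidence.

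The protocol itself expects sites to differ. Its cost-effectiveness section names fluconazole stock-outs and variable performance and acceptance of lumbar puncture, and says loss to follow-up will probably differ by site. An ICC of zero does not fit that expectation.

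At stake is whether ordinary site-to-site variation could be read as the effect of a training package, a reporting scheme or a rural setting, in a study meant to guide a national programme.

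**Working it through.** **1. The plan's own figure.** Inputs (section 8.1): 900 controls, 300 high-titre patients, control survival 0.70, two-sided alpha 0.05.
- High-titre survival: 0.70^1.37 = 0.613 and 0.70^1.44 = 0.598.
- Control events: 900 × 0.30 = 270. High-titre events: 300 × (1 − 0.613) = 116.0 and 300 × (1 − 0.598) = 120.5.
- Power = Φ(ln HR / √(1/d₁ + 1/d₀) − 1.96).
- HR 1.37: Φ(0.3148/0.1110 − 1.96) = 80.9%.
- HR 1.44: Φ(0.3646/0.1096 − 1.96) = 91.4%.
- A two-proportion calculation gives 78.7% and 89.6%.

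The stated figures therefore reproduce with independent patients and a design effect of 1. Titre varies between patients within a clinic, so this is a reasonable basis for that contrast.

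**2. Patients per clinic.** Section 8.2 expects 6000-8000 asymptomatic CRAG+ cases a year, and section 3 gives 4500 clinics nationally. That is 1.3-1.8 per clinic-year, or 2.7-3.6 over two years if the 400 surveillance clinics have average volume. I use 3.

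**3. Between-unit contrasts.** The documents give no ICC (ρ), so 0.01-0.10 is assumed. With m patients per unit:
- Design effect (DEFF) = 1 + (m − 1)ρ.
- The correct interval is √DEFF times as wide as the unadjusted one.
- Type I error of the unadjusted test = 2[1 − Φ(1.96/√DEFF)].

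| Unit | m | DEFF, ρ = 0.01 / 0.05 / 0.10 | Type I error |
|---|---|---|---|
| Clinic, average volume | 3 | 1.02 / 1.10 / 1.20 | 5.2% / 6.2% / 7.4% |
| Clinic, higher volume | 20 | 1.19 / 1.95 / 2.90 | 7.2% / 16% / 25% |
| District | 60 | 1.59 / 3.95 / 6.90 | 12% / 32% / 46% |

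The district row splits 1200 patients over 20 districts. Both numbers are assumptions: 1200 is borrowed from the titre example, and the number of surveillance districts is not stated. As a cross-check on district size, section 1.1 reports 1271 CRAG+ patients over three years, which section 8.2 places in 4 districts: 1271/(4 × 3) ≈ 106 per district-year. At m = 106 the type I error is 17%-56%.

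Beta-binomial simulation (1200 patients, 30% risk in both groups, half the units exposed) agrees to within one or two points: about 5%-8% for 400 equal clinics and about 13%-45% for 20 equal districts. With unequal clinic sizes (coefficient of variation 1), the 400-clinic figure rises to 11%-12% at ρ = 0.10. A cluster-robust test in similar simulations rejected 4.7%-7.2% of the time.

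**4. Pre/post in the same facilities.** Let m be patients per facility-period and f the share of site variance specific to a period. The true variance of the difference, divided by the variance that assumes independence, is 1 − ρ + mfρ. With 20 sites, m = 30 and ρ = 0.05:
- f = 0: ratio 0.95, type I error 4.4% (slightly conservative).
- f = 0.2: ratio 0.95 + 0.30 = 1.25, type I error 8.0%.
- f = 0.5: ratio 0.95 + 0.75 = 1.70, type I error 13%.

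The direction turns on whether mf exceeds 1, which the protocol does not allow one to judge.

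**The case against.** **The detectable-HR table is not an intervention calculation.** A reader might infer that the Years 2-5 interventions were powered as though patients were independent, or that 1.37 and 1.44 are too optimistic. Neither follows. The table is for subgroups, its sole contrast is a patient-level factor, and no power is claimed for any intervention. This stands in full.

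**Independence is read from silence.** Section 8.1 names no test or variance estimator for the intervention comparison, and a separate SAP may supply one. This stands in part: it cannot be said that the protocol prescribes an independent-patient test. But section 8.1 does fix the comparison as one of period rates and gives clustering to one subgroup only. Nothing in it leads a later analyst to treat the other facility-level contrasts differently.

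**Not every intervention is facility-wide, and none is final.** Lumbar puncture accepted versus declined, SMS to individual patients and titre-based therapy are patient-level, and section 3 makes the choice depend on the baseline findings. This stands. A blanket cluster rule would be wrong, and a detectable difference cannot be fixed yet.

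**The sentence on comparing rates describes before and after.** With stable site effects, ignoring the pairing does not inflate error. This stands for that case. It does not cover period-specific site changes or the between-unit comparisons planned in section 3.

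**Clinics are small.** At about 3 patients per clinic the inflation is slight. This stands for average clinics, not for districts or high-volume sites.

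**Conclusion.** The point holds for contrasts whose exposure is set at facility or district level: training, patient education, Result for Action reports, urban/rural and LP-performing clinics. Following section 8.1 without adjustment gives intervals that are too narrow for between-unit comparisons. Type I error is about 5%-8% at 3 patients per clinic with equal sizes, up to 11%-12% with unequal sizes, and about 13%-45% for 20 districts of 60. For pre/post in the same facilities, the intervals are slightly too wide if site effects are stable and too narrow if they shift between periods.

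These sizes rest on an assumed ICC of 0.01-0.10, a 30% event rate, and assumed unit numbers and sizes. The documents do not support the broader claims that every Years 2-5 result would be falsely precise or that the titre hazard ratios are wrong. This is worth correcting before the first intervention is evaluated.

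**What to change.** In section 8.1:

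- State that any contrast whose exposure is set at facility or district level is analysed with that unit as the cluster. Suitable models are a mixed model or GEE for 6-month status, or Cox regression with shared frailty or cluster-robust variance. Add a small-sample correction when units are few. Use district as the cluster where the exposure is assigned by district.
- For pre/post, keep facility and period effects with a facility-by-period term instead of comparing two pooled rates. Name the concurrent comparison with facilities lacking the intervention, which section 3 already plans.
- Give cluster-robust confidence intervals for the overall rates.
- Label the detectable-HR table as applying to patient-level contrasts only.
- Once interventions are chosen, state the detectable difference from the number of facilities or districts, using the ICC estimated in Years 1-2.
- Say that patient-level interventions need no cluster-level exposure analysis.

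The cost is wording, slightly more analysis work, and wider intervals with less favourable detectable effects for the cluster-level contrasts. No extra patients are needed, and the clinic can be identified from the data already planned.

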- 3) Integration with WHO universal HIV test-and-treat guidelines: South Africa adopted the WHO universal HIV test-and-treat guidelines in September 2016. While the National Department of Health has indicated that a baseline CD4 count should be ordered for all patients starting ART, in practice many patients are initiated on ART on the same day as HIV diagnosis, well before the baseline CD4 and reflex CrAg results are available. In KwaZulu-Natal, the provincial department has recently recommended routine same-day ART initiation at all its facilities.

It is unknown if same-day ART initiation among those with advanced HIV would have an adverse impact on patient outcomes at a programmatic level (as a result of unmasking IRIS). Conversely, even reflex CRAG screening may potentially delay ART initiation for those who ultimately screen CRAG negative but should be fast tracked onto ART to reduce risk of HIV progression and other OIs. We have previously described shorter median times to ART initiation amongst those CRAG-screened compared to those not screened (32).

- 4) Impact of training: We have previously implemented training workshops for health care providers (doctors, nurses, pharmacists, counsellors) with the goal of improving clinical management of cryptococcal disease. However the impact of these workshops on patient outcomes has not been measured.
- 5) Optimal treatment regimen for asymptomatic CRAG+ persons. Although CRAG+ persons receiving fluconazole generally do better than if not treated at all, 25%-30% go on to develop meningitis or die despite the WHO-recommended antifungal therapy and ART. A 2.9-fold worse survival was observed in asymptomatic CRAG+ vs. CRAG- persons with CD4 count <200 cells/µL in Tanzania and Zambia (33) (Figure 7).

The current WHO regimen for asymptomatic CRAG+ patients was based on expert opinion and extrapolated from management of symptomatic cryptococcal meningitis.

This regimen likely requires further refinement. As an example, preliminary results from the ORCAS trial in Uganda suggest that persons with CRAG titres \geq 160 and CD4 count <50 cells/µL are more likely to develop subsequent cryptococcal meningitis compared with those with a lower CRAG titre/ higher CD4 count when receiving current WHO-recommended antifungal therapy. Customized or more intensive therapy for those with high titres may be a useful strategy to reduce CRAG+ mortality (**Figure 8**).

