3 STUDY DESIGN

This is an evaluation of an ongoing national screening programme. In years 1 and 2, we will implement an enhanced metrics and evaluation project at selected sites in all provinces across South Africa to measure 6-month outcomes of this programme, along with operational challenges. In years 2 to 5 we will implement programmatic strategies to maximize 6-month cryptococcal meningitis-free survival.

Per South African standard of care, those with a CD4<100 cells/µL will reflexively get a CRAG test performed on remaining blood specimen. We expect the majority of these persons to be asymptomatic outpatients presenting for routine HIV care, though a small proportion will be persons who present to care because they feel unwell. All participants will receive standard of care treatment for asymptomatic cryptococcal antigenaemia, per South African HIV guidelines.

Primary Objective (years 1 and 2): To implement enhanced surveillance at selected sites to determine the outcomes (overall and for pre-specified subgroups) of a national reflex laboratory CRAG screening and pre-emptive treatment programme in South Africa. We estimate performing enhanced surveillance at **approximately 400 clinics out of 4500 clinics nationally**. A list of surveillance facilities will be agreed upon in discussion with provincial departments of health.

We will assess the cascade of care from CD4 testing to CRAG testing, to receipt of CRAG results by healthcare provider, assessment for symptoms, lumbar puncture if indicated, preemptive treatment for those asymptomatic, and 6-month outcomes.

The initial surveillance performed in Objective 1 will establish **baseline 6-month CRAG+ outcomes** (Year 1 and 2) from which subsequent programmatic interventions will seek to improve.

Subgroup Analyses

A number of subgroup analyses will be performed to understand optimal CRAG screening and treatment programmes. For example, we will compare outcomes amongst CRAG+ persons who:

- a) initiated on ART before CD4/ CRAG results are known (same-day ART initiation in the context of universal HIV test-and-treat) to those who have ART delayed until a minimum of 2 weeks of antifungal treatment completion
- b) rural clinics vs. urban centres
- c) high titres (\geq 160) vs. low titres (<160)

- d) clinics that routinely perform lumbar punctures to those that are unable to perform lumbar punctures (stratified by titre)

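### Section 8.1 analyses the Years 2-5 primary objective only as a before/after comparison, with Year 2 in both periods and the planned non-intervention facilities left out

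*Protocol*

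**What the plan says.** **Baseline.** Section 8.1 says the primary and secondary event rates will be "estimated overall and for pre-specified subgroups during the first 2 years of the study". Section 3 agrees: its baseline outcomes are those of "Year 1 and 2) from which subsequent programmatic interventions will seek to improve".

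**Intervention period.** The Protocol Summary and the opening of Section 3 both place the programmatic interventions in Years 2 to 5. Section 3 adds, on how they will be chosen: "Starting in Year 2, we will use the data generated from the preceding years".

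**Comparison in the analysis section.** Section 8.1 gives one contrast for this objective: "Those rates will subsequently be compared with the rates after programmatic changes have been made (during years 2-5". It mentions no concurrent comparator.

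**Comparison in the design section.** Section 3 is broader. It says "Such interventions will be implemented at selected enhanced surveillance facilities", and that the aim is "to determine their effectiveness (pre/post intervention) as well as compared with facilities without the intervention". Under Intervention 3 it repeats a with/without comparison for the Result for Action reports.

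**Background.** Section 1.1 (knowledge gaps, item 3) states that "South Africa adopted the WHO universal HIV test-and-treat guidelines in September 2016". It reports that many patients in practice start ART on the day of diagnosis, that one province has recently recommended this at all its facilities, and that the effect on outcomes at programme level in advanced HIV is unknown.

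**The concern.** Improving 6-month cryptococcal meningitis-free survival through interventions in Years 2-5 is one of the protocol's two primary objectives. Two features of 8.1 can bias its answer.

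First, a facility that starts an intervention during Year 2 contributes exposed patients to a baseline that covers all of Years 1 and 2. Those patients pull the baseline towards the post-intervention rate, so a real effect looks smaller than it is.

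Second, a comparison of two calendar periods cannot separate the intervention from anything else that changed between them. A favourable drift would be read as benefit and an unfavourable one would hide it. The protocol names a candidate itself: same-day ART is still spreading, and Section 3 lists it among possible risk factors for treatment failure.

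Section 3 supplies the comparator that could deal with the second problem, but 8.1 does not use it. Neither section says how the pre/post and between-facility contrasts are to be combined, or which one decides if they disagree.

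**Working it through.** **1. The plan's own figures.** The protocol gives no power or precision figure for the before/after comparison. Its only such figures, in 8.1, concern the titre subgroups (300 vs 900, 70% event-free survival in controls). They reproduce acceptably: survival in the high-titre group is 0.70^1.37 = 0.613, and a two-proportion calculation gives 78.7% power against the stated 80%. At HR 1.44 it gives 89.6% against 90%. They have no bearing on this point beyond supplying the 70% used below.

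**2. Which interventions could begin in Year 2.** Section 3 puts routine titre reporting (Intervention 1) and enhanced therapy (Intervention 4) after the Year 1-2 data. Training (Intervention 2) and SMS or results-for-action reports (Intervention 3) carry no such delay. Exposure within the baseline is therefore possible, but not certain.

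**3. Effect of exposed patients in the baseline.** Let c be the share of baseline patients already exposed.

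- Inputs: unexposed survival 0.70 (protocol, subgroup assumption); exposed survival 0.78 (assumed); c (assumed).
- Baseline = 0.70(1 - c) + 0.78c. Measured gain = 0.78 - baseline = 0.08(1 - c).

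| c | Baseline | Measured gain |
|---|---|---|
| 0 | 0.70 | 8 points |
| 0.25 | 0.72 | 6 points |
| 0.50 | 0.74 | 4 points |

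With equal accrual in the two years, c is half the share of Year 2 patients who are exposed. So c = 0.25 means half of them, and c = 0.50 means every baseline patient came from a facility exposed for all of Year 2. That is the ceiling.

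The loss in sample-size terms, for an assumed rise from 70% to 80% at 80% power and two-sided alpha 0.05 (two proportions, no clustering): 294 per period at c = 0, 505 at c = 0.25, and 1094 at c = 0.50.

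**4. Effect of calendar drift.** If survival drifts by d points between the periods for reasons unrelated to the study, the before/after difference is roughly the diluted effect plus d. With no intervention effect, 1,200 patients per period (assumed), a 70% start and no clustering, the chance of a significant improvement is about 19% for d = 2 points, 37% for d = 3 and 78% for d = 5. The protocol gives no value for d.

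**5. Follow-up that spans the start date.** The endpoint takes 6 months. A patient who tests positive less than 6 months before a facility's start date is followed into the intervention period, so a start date alone does not separate the periods cleanly.

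**6. Price of the controlled contrast.** With four equal, independent cells of variance v, a before/after difference has variance 2v and a difference of two such differences has 4v. The ratio of standard errors is sqrt(4v/2v) = sqrt(2) = 1.41.

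**The case against.** The strongest reply is that 8.1 should be read with Section 3. A reader of 8.1 alone might infer that the study has no control at all. The documents do not support that: Section 3 plans a comparison with non-intervention facilities and repeats one for the Result for Action reports. The omission is in 8.1, not in the protocol as a whole.

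The overlap can also be read kindly. Section 8.1 speaks of rates after changes have been made, and Section 3 of pre/post intervention. Both could be anchored to the change itself rather than the calendar year. Two of the four example interventions wait for the Year 1-2 data, and only selected facilities are involved. This stands to the extent that dilution is a risk and not an established fact. It does not supply a rule for Year 2 patients.

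Two further inferences are tempting and should not be drawn:

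- That facilities are chosen for poor results and would improve by regression to the mean. Section 3 ties the choice of intervention, not of facility, to the problems observed. The only selection criterion it gives is volume, for Intervention 4.
- That reflex screening was still being introduced during the baseline. Section 1.1 says it was in place at all public-sector CD4 laboratories on 1 November 2016. Test-and-treat had been adopted in September 2016. Neither dated change is shown to fall between the two periods, so the drift argument rests on continuing uptake of same-day ART.

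Finally, model details may fairly be left to a statistical analysis plan that is not at hand. The objection here is to what the protocol does state: overlapping periods, and an analysis narrower than its own design.

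**Conclusion.** The point holds within these limits. As written, 8.1 assigns Year 2 to both periods and analyses a primary objective by calendar comparison alone, although Section 3 plans a concurrent comparator. Followed literally, it can place exposed patients in the baseline and cannot separate drift from effect.

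The size is illustrative. Dilution multiplies the true effect by (1 - c), at most a halving: 8 points becomes 6 at c = 0.25 and 4 at c = 0.50. Drift enters one for one, in either direction. The 78%, the exposure shares, the drift and the 1,200 per period are assumptions. Only the 70% is in the protocol, where it is a subgroup assumption. How much dilution or drift will actually occur cannot be determined from the document.

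**What to change.** Rewrite the comparison paragraph in 8.1, before the first intervention starts, to say:

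- **Periods.** Pre and post are defined by each facility's own intervention start date, and no patient counts in both. Comparator facilities take the same calendar date.
- **Spanning follow-up.** State one rule for patients whose 6 months cross the start date. For example, classify by date of the CRAG-positive specimen and leave those who tested positive in the preceding 6 months out of the primary contrast, at intervention and comparator facilities alike.
- **Primary estimate.** The change in 6-month meningitis-free survival at intervention facilities minus the change over the same calendar period at non-intervention surveillance facilities, allowing for clustering by facility. The simple before/after difference becomes descriptive.

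The cost is one paragraph and no new type of data, because Section 3 already plans the comparator facilities, though their surveillance must run through the intervention years. The interval is about 1.4 times wider than for the simple contrast if the cells are equal and independent, and the ratio will differ with unequal cells or clustering. The example rule for spanning follow-up also gives up to 6 months of accrual per facility. The controlled contrast removes only drift that both groups of facilities share, and 8.1 should state that assumption.
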